1.0 PROTOCOL SUMMARY AND/OR SCHEMA

This is a double-blinded, randomized trial. Its purpose is to compare the steroid cream mometasone furoate 0.1% (MF), with standard emollient skin care, Eucerin, on the prevention of grade 2 or higher skin toxicities in breast cancer patients receiving PMRT to the chest wall and regional lymph nodes. Patients will be stratified based on two variables: the presence of a reconstruction in order to achieve a balanced population of patients being treated with either photon or electron beams, and body mass index (BMI <30 vs ≥30).

Female breast cancer patients who have received mastectomy + axillary surgery and will undergo postmastectomy radiation (PMRT) at our institution are eligible for this study. Enrollment of 143 patients is expected to take place over 3 years.

Skin toxicities using the Common Terminology Criteria for Adverse Events (CTCAE) v.4 scale will be scored by evaluating RN or MD . Assessments will be completed at baseline, weekly during radiation therapy (RT), and 10-14 days following the completion of RT. Patient-reported skin symptoms will also be assessed at baseline, at week 5 of RT, and 10-14 days following completion of RT.

Screening	Randomization	Pre-RT	Weekly During RT (5 weeks, 50 Gy)	Follow-up (10-14 Days Post-RT)
143 breast cancer patients status post mastectomy + axillary surgery, ± chemotherapy 
 Stratifications: 
 Reconstruction Yes vs no Body Mass Index <30 vs ≥30 	Eucerin BID 
 or mometasone furoate 0.1% BID 	
 Baseline H and P Baseline Provider Skin Toxicity Assessment Baseline Skindex-16 questionnaire Patient education on topical cream usage 	
 Weekly status checks Weekly skin cream compliance assessed Provider Skin Toxicity Assessment Skindex-16 questionnaire during Week 5 of RT 	
 Skin cream compliance assessed Provider Skin Toxicity Assessment Skindex-16 questionnaire

2.0 OBJECTIVES AND SCIENTIFIC AIMS

Primary Objective

- To determine if MF, as compared to Eucerin, is effective in preventing grade 2 or higher radiation dermatitis, particularly moist desquamation and/or moderate to brisk erythema in women receiving PMRT

Secondary Objectives

- To compare patient-reported skin symptoms between interventions
- To determine maximum reported skin toxicity and the time to occurrence

3.0 BACKGROUND AND RATIONALE

3.1 Benefit of Postmastectomy Radiation

PMRT is an essential component of treatment for locally advanced breast cancer. The publication of the Oxford Overview meta-analyses of randomized clinical trials in 2005 showed that, compared with surgery alone, the addition of PMRT after mastectomy both reduced the rate of local cancer recurrence and improved 15-year breast cancer mortality by 5% (Clarke, Collins et al. 2005). Although the clinical benefits of PMRT are well established, there is a paucity of data available on the acute toxicities of PMRT, namely, skin toxicities. The majority of studies that examine quality of life after mastectomy focus primarily on cosmetic and psychosocial issues.

3.2 Radiation-Induced Dermatitis

A variety of patient and treatment-related factors such as fractionation schedules, dose, size of the treatment field, concurrent chemotherapy, use of bolus or other beam-modifying devices, and individual genetic variation can affect the intensity of the skin reaction to radiation (Tucker, Turesson et al. 1992). The majority of data available regarding side effects are generated from patients receiving radiation to the intact breast, not the chest wall after mastectomy. Side effects are generally categorized as acute if occurring during or within 6 weeks of radiation treatment and late if occurring >6 weeks after completion of treatment. A common acute toxicity is dermatitis within the irradiated volume. Typically, the skin becomes erythematous and/or hyperpigmented, and may desquamate, in particular in the area of skin folds such as the axilla, supraclavicular fossa, or inframammary fold. Desquamation may be dry or moist. Progressive erythema may be seen after 10-20 Gy, depending on the fractionation schedule (Turesson and Notter 1975), and reaches maximal intensity approximately 1-2 weeks following the completion of treatment. An example of the development of moist desquamation and grade 2 erythema in a woman 1 week post-completion of PMRT to an unreconstructed chest wall is illustrated in Appendix 3.

Factors contributing to variation in the severity of dermatitis in patients receiving PMRT have not been well studied. Acute skin toxicities are generally more severe in the setting of PMRT than breast conservation therapy (BCT), as the skin itself is considered part of the radiation target with PMRT. There are remarkably little data available on the incidence of radiation dermatitis in the post-mastectomy chest wall setting. The three large randomized trials investigating the use of PMRT either do not report toxicity or report late toxicity excluding skin toxicities (Overgaard, Hansen et al. 1997; Overgaard, Jensen et al. 1999; Ragaz, Olivotto et al. 2005). One small retrospective series of 89 patients receiving PMRT using an electron technique reported that 19 patients developed dry desquamation, and only five developed moist desquamation (Hehr, Budach et al. 1999). In contrast, a series of 118 patients treated with a similar technique reported that 52% of patients developed grade 3-4 skin toxicity by Radiation Therapy Oncology Group (RTOG) criteria, and 31% of patients required an unplanned treatment break to recover from early radiation-induced skin toxicities (Spierer, Hong et al. 2004).

The development of normal tissue toxicities in breast cancer patients receiving adjuvant external beam RT demonstrates significant heterogeneity among individuals (Twardella, Popanda et al. 2003), which can be attributed to a variety of individual, tumor stage, cellular, and molecular factors. Increasing evidence suggests that individual genetic variations may also play a significant role in the development of adverse radiation responses (De Ruyck, Van Eijkeren et al.

2005; Andreassen, Alsner et al. 2006; Alsbeih, El-Sebaie et al. 2007), but these remain poorly understood. Existing estimates on rates of radiation dermatitis are extrapolated from patients with intact breasts, who have been treated with a variety of techniques that affect the development of dermatitis. A randomized trial investigating the use of intensity-modulated RT (IMRT) in the setting of BCT demonstrated moist desquamation in 31.2% receiving IMRT and 47.8% with standard treatment, respectively (Pignol, Olivotto et al. 2008). The primary factor that predisposed to moist desquamation was large breast size; race-ethnicity and genetic factors were not assessed in this Canadian study. In Table 1, we summarize the results from the few studies that have specifically evaluated skin toxicities in breast cancer patients who have received PMRT.

Table 1. Incidence of RT-Related Adverse Reactions in PMRT Patients

Sample Size	Skin Toxicities	Study Variables	References
41 PMRT patients	Late tissue fibrosis and telangiectasias	XRCC1&3, TGFB1, SOD2, APEX SNPs	Andreassen et al., 2003
118 PMRT patients	52% grade 3-4 acute skin toxicity	-	Spierer et al., 2004
89 PMRT patients	19 dry desquamation; 5 moist desquamation	-	Hehr et al., 1999

3.3 Evidence for Topical Agents' Prevention and Treatment of Radiation-Induced Dermatitis

Acute radiation dermatitis has been attributed to the combined result of a decrease in functional stem cells, changes in the skin's endothelial cells, inflammation, cell necrosis, and death (Hymes et al. 2006). Proposed mechanisms for the anti-inflammatory effect of corticosteroids include vasoconstriction, decreased capillary permeability, and inhibition of leukocyte proliferation and migration (Yohn, 1990). However, all mechanisms are not fully elucidated.

At the present time, there are no established standards for either the prevention or management of radiation-induced skin reactions. Intervention is primarily based on clinician experience. Numerous products are used by various radiation oncology departments throughout the world. Biafene cream (Ortho-McNeil Pharmaceuticals, Titusville, NJ, USA) was evaluated in a multicenter randomized trial conducted by the RTOG and was not found to be superior to standard regimens in the prevention of radiation-induced skin reactions (Fisher, Scott et al. 2000). Generally, it is agreed that a key element of the prevention of radiation dermatitis is moisturizing the irradiated area with Eucerin, Aquaphor, aloe vera, or other hydrophilic products (Maddocks-Jennings, Wilkinson et al. 2005). The emphasis has been on teaching self care to minimize skin trauma, irritation, and or/infection. In our department, we recommend the application of Eucerin BID to the breast or chest wall as standard care for our breast cancer patients. Moist desquamation is treated with Silvadene cream or hydrocolloid dressings.

To date, five trials have evaluated topical corticosteroids for the prevention of acute skin reactions in patients receiving radiation (Bostrom, Lindman et al. 2001; Schmuth, Wimmer et al. 2002; Shukla, Gairola et al. 2006; Omidvari, Saboori et al. 2007; Miller, Schwartz et al. 2011).

MEMORIAL SLOAN-KETTERING CANCER CENTER
IRB PROTOCOL

IRB#: 13-069 A(1)

The details and results of these studies are summarized in Table 2; however, these studies collectively demonstrated that topical corticosteroid agents used as the sole skin care regimen during irradiation reduced the severity of skin reactions following RT.

Table 2. Select Trials of Topical Steroidal Creams in Breast Cancer Patients Receiving Radiation Therapy

Study (Year)	Study Population, Targeted	Corticosteroid Agent	Outcomes
Bostrom et al, 2001	N=49, whole breast	Mometasone furoate 0.1% vs Placebo	MMF group with significantly decreased acute radiation dermatitis (P=0.0033).
Schmuth et al, 2002	N=36 ,whole breast	0.1% methylprednisolone cream vs 0.5% dexamethasone cream vs no intervention	No significant difference in mean severity scores of radiation dermatitis
Shukla et al, 2006	N=60, whole breast	Beclomethasone dipropionate spray vs no intervention	Corticosteroid group with significantly reduced incidence of moist desquamation
Omidvari et al, 2001	N=51, chest wall	Betamethasone 0.1% vs placebo vs no intervention	Steroid arm with significantly delayed occurrence of ARD
Miller et al, 2011	N=176; 140, whole breast; 29, chest wall	Mometasone Furoate 0.1% vs Placebo	No difference in the mean maximum grade of radiation dermatitis

Mometasone furoate is a medium-strength topical steroid that has a low atrophogenic potential, and has demonstrated greater anti-inflammatory activity and a longer duration of action than other medium-strength topical steroids such as betamethasone (Prakash & Benfield, 1998). MF has been shown to be effective in reducing clinically appreciated radiation dermatitis and pruritus in patients who are receiving whole breast radiotherapy in several randomized trials comparing MF with a placebo emollient (Bostrom, Lindman et al. 2001; Miller, Schwartz et al. 2011). However, its applicability in patients who have undergone mastectomy and receive irradiation of the chest wall has not been established. Only one of these studies included patients who received chest wall radiotherapy but, because the sample size was so small, they were unable to draw definitive conclusions regarding the benefit of MF in this population (Miller et al., 2011). The aim of this study is to elucidate the effect of mometasone furoate versus standard of care on patients receiving post-mastectomy irradiation, specifically.

3.4 Patient-Reported Outcomes and Provider Assessment Tools for Radiation Dermatitis

Currently, the most widely used standardized method of recording provider-assessed toxicities is the CTCAE version 4. CTCAE has been shown to result in stable assessments of toxicities among practitioners (Trotti, 2003). Using this assessment tool, grade ≥ 2 radiation dermatitis encompasses an assessment of both the degree of erythema and desquamation, as gauged by the provider. Grade 2 erythema is defined as “moderate to brisk,” and grade 2 MD is defined as “patchy, mostly confined to skin folds and creases” (CTCAE v4.03, 2009).

There is evidence that patients and clinicians differ in their assessment of the severity of subjective skin toxicities (such as pruritus) during radiation (Neben-Wittich M. A., 2011). The Skindex-16 is a tool designed to capture patient-reported assessments of subjective adverse effects. Skindex-16 is comprised of sixteen questions, which are sub-categorized into an emotional subscale (six questions), a functional subscale (five questions), and a symptom subscale (five questions). Rankings of the questionnaire are then averaged to obtain a score of severity of patient-reported outcomes. This allows providers to gauge which aspects of the patient’s experience are most affected by the treatment.

The Fitzpatrick Skin Classification is a well-recognized tool for patients’ initial assessment of their general level of skin sensitivity. The scale ranges from category I to VI, representing a range from pale skin/always burns to dark skin/never burns (Fitzpatrick TB, 1988).

4.0 OVERVIEW OF STUDY DESIGN/INTERVENTION

4.1 Design

This is a Phase III double-blinded, randomized trial. Its purpose is to compare MF 0.1%, a steroid cream, with standard emollient skin care, Eucerin, on the prevention of acute grade 2 or higher skin toxicities in breast cancer patients receiving PMRT to the chest wall and regional lymph nodes. We hypothesize that MF will prevent moderate to severe radiation dermatitis in women undergoing chest wall irradiation for breast cancer.

4.2 Intervention

Eligible patients will receive skin care according to their randomization assignment during radiation therapy. Skin toxicity assessments and assessment of patient-reported compliance will be done on a weekly basis while the patient is receiving RT, by the RN or physician utilizing CTCAE 4.0 and the weekly status check form, as per current standard practice. Patient-reported skin toxicities will be measured using the Skindex-16 assessment tool. Patients will report Fitzpatrick Skin Category at the time of the History and Physical.

Patients will be followed at 10-14 days after the completion of treatment during which time they will have a provider skin assessment and they will complete an additional Skindex-16 Assessment.

5.0 THERAPEUTIC/DIAGNOSTIC AGENTS

5.1 Mometasone Furoate

Class: Anti-inflammatory agents

ATC Class: D07AC13

VA Class: DE200

Chemical Name: 9 α ,21-dichloro-11 β ,17-dihydroxy-16 α -methyl-17(2-furanylcarbonyl)pregna-1,4-diene-3,20-dione

Molecular Formula: C₂₇H₃₀Cl₂O₆

CAS Number: 83919-23-7

Brands: Elocon

Topical MF is a medium-potency corticosteroid that modifies the body's immune response by suppressing the formation, release, and activity of endogenous mediators of inflammation, including prostaglandins, kinins, histamines, liposomal enzymes, and the complement system. It is available in a 0.1% cream, lotion or ointment form. Indications for topical use include relief of inflammatory and pruritic manifestations of corticosteroid-responsive dermatoses. MF has a low atrophogenic potential, and a longer duration of action than other topical steroids in its class.

5.2 Eucerin Original cream

Eucerin Original is a hydrous lanolin emollient skin cream, which is used to soften and moisturize the skin. Emollients may be used as lubricants to treat or prevent dry, itchy skin, and minor skin irritations.

5.3 Skindex-16 Assessment Module

The usefulness of patient-reported outcomes as an alternate means to measure side effects has been reported in the literature (Huschka, Mandrekar et al. 2007). The Skindex-16 is an analog scale of symptoms and functional endpoints related to skin toxicity that can occur in the treatment area, and has been assessed for reliability: scale scores were reproducible after 72 hours, and demonstrate both content and construct validity (Chren, Lasek et al. 2001). It has been used for patients to rate skin conditions that have occurred within the previous week. It consists of a short 16-item assessment completed by the patient, using numerical analogue scales (0 = never bothered to 6 = always bothered). Responses to the Skindex-16 are categorized into three subscales: symptom, emotional, and functional (Appendix 1).

6.0 CRITERIA FOR SUBJECT ELIGIBILITY

6.1 Subject Inclusion Criteria

- Age \geq 18 years
- Stage 1-3 invasive breast cancer that is histologically confirmed at MSKCC
- Status post mastectomy with axillary exploration (sentinel node biopsy and/or axillary lymph node dissection) to receive PMRT
- ECOG Performance Status of 0 or 1

6.2 Subject Exclusion Criteria

- Male
- Patients with distant metastasis or locally recurrent breast cancer
- Patients who are pregnant or breastfeeding
- Prior radiation therapy to the ipsilateral chest wall or thorax
- Patients requiring a chest wall boost
- Concurrent chemotherapy (biologic agents are allowed)
- Psychiatric illness that would prevent the patient from giving informed consent
- Inability or unwillingness to comply with skin care instructions and follow-up
- Allergy to either Eucerin or MF• Residual grade >1 skin toxicity, cellulitis, or incompletely healed wound(s) at intended site of study drug application at simulation
- Medical condition such as uncontrolled infection (including HIV), uncontrolled diabetes mellitus, or connective tissue diseases (lupus, systemic sclerosis, or other collagen vascular diseases)
- Treatment with non-standard, inverse-planned Intensity Modulated Radiation Therapy (IMRT), palliative or pre-operative radiation

7.0 RECRUITMENT PLAN

All female patients who received a mastectomy and plan to receive PMRT at MSKCC will be eligible for screening. Potential participants will be identified by the protocol investigators or the departmental breast research team.

Approximately 120-150 breast cancer patients receive PMRT in the Department of Radiation Oncology in the Main Campus per year. On average, 15-20 mastectomy patients are under treatment at any moment, thus providing a large pool of patients who could be eligible for this study. We estimate treating 70-80 eligible patients at the Main Campus per year, which would enable us to reach our accrual goal of 143 patients within 3 years.

8.0 PRETREATMENT EVALUATION

The History and physical exam in Radiation Oncology will include information on race/ethnicity, age, body mass index, chemotherapy status, hormone therapy, smoking history/status, diabetes, high blood pressure, Eastern Cooperative Oncology Group (ECOG) performance, and reconstruction status.

Radiation Treatment Planning will be approved by the treating MD, in order to determine type of chest wall radiotherapy (photons vs electrons) to be administered, as outlined in section 9.1.

Baseline Provider Skin Toxicity Assessment will be done within 14 days prior to the start of RT.

Patients will complete a baseline Skindex-16 Questionnaire and Fitzpatrick Skin Classification within 14 days prior to the start of RT (Appendix 1 and 2).

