14.0 BIOSTATISTICS

This is a double-blinded, randomized trial (see Section 15.2 for details of randomization) to compare MF 0.1% cream with standard skin care (Eucerin) on the prevention of moderate to severe skin toxicities in breast cancer patients receiving post-mastectomy radiation to the chest wall and regional lymph nodes. A patient is deemed to have developed skin toxicity if she has a grade ≥ 2 skin toxicity as defined in Section 3.4 within 7 weeks from the beginning of radiation.

Based on estimates provided by radiation oncologists at our institution, the rate of grade ≥ 2 toxicity using Eucerin as skin care for chest wall radiation is $\approx 50\%$. This estimate is slightly lower than the findings from the Spierer study cited in section 3.2, to reflect this study's inclusion of patients treated with photons (in the presence of reconstruction) as well as electrons. We expect that the usage of MF can reduce this rate to 25%. 124 evaluable patients are needed for the comparison, with 62 patients in each arm. Two-sample, two-sided proportion tests will be used to derive the statistical significance. One interim analysis will be conducted when 31 patients in each arm have been enrolled and evaluated using the O'Brien-Flemming procedure, which will declare significance if the test p-value is less than 0.005. Correspondingly the final analysis will declare significance if the test p-value is less than 0.048. This design has a power of approximately 0.83 (i.e., detecting the true toxicity rate of 25% or lower) at the type I error (i.e., declaring MF more effective while it yields the same toxicity rate as Eucerin) rate of 0.05 based on 100000 statistical simulations.

All deaths unrelated to the toxicities, and patients lost to follow-up (before toxicities can be evaluated), will be excluded from the comparison and new patients will be accrued for replacement. To this end we plan to enroll an additional 15% of patients. Therefore our final proposed accrual is about 143 patients, which is expected to be done in 3 years.

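### The primary comparison is unadjusted: it uses neither the randomisation strata (reconstruction, BMI) nor the Fitzpatrick category collected from every patient

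*Combined protocol and SAP*

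**What the plan says.** Fitzpatrick category is planned for everyone at baseline. Section 8.0: "Patients will complete a baseline Skindex-16 Questionnaire and Fitzpatrick Skin Classification within 14 days prior to the start of RT". Section 4.2: "Patients will report Fitzpatrick Skin Category at the time of the History and Physical". The schedule in Section 10.2 also lists it, at simulation. Section 3.4 presents it as the patient's own rating of general skin sensitivity: "The scale ranges from category I to VI, representing a range from pale skin/always burns to dark skin/never burns".

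The primary outcome is grade ≥2 skin toxicity within 7 weeks of starting radiation. Section 3.4 says that grade ≥2 "radiation dermatitis encompasses an assessment of both the degree of erythema and desquamation", and Section 2.0 names both components.

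Section 14.0 gives the primary analysis in one sentence: "Two-sample, two-sided proportion tests will be used to derive the statistical significance". The strata in Sections 1.0 and 15.2 are reconstruction (yes/no) and BMI (<30 vs ≥30); Fitzpatrick category is not one. Section 14.0 names neither these strata nor Fitzpatrick category in any analysis. The only covariate adjustment it describes is an optional analysis of covariance for Skindex-16. Cox models are mentioned for time to toxicity, with no covariates listed.

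**The concern.** Two kinds of baseline information are available and unused. The strata were chosen because the investigators wanted them balanced. A test that ignores them does not credit that balance, and it is somewhat conservative if they predict the outcome. Fitzpatrick category is the one instrument the protocol uses to measure skin sensitivity before treatment, and moderate to brisk erythema is enough on its own for a primary event. An association is therefore plausible.

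Two things are at stake: some power if skin type is strongly prognostic, and protection if the arms differ in skin type by chance. Nothing in the design limits such an imbalance, either at 62 per arm or at the 31-per-arm interim, where the trial may declare significance. If an imbalance appears and no adjusted analysis was pre-specified, one chosen after seeing the data will carry little weight.

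**Working it through.** **Inputs from Section 14.0.** Rates 50% (Eucerin) and 25% (MF); 62 evaluable per arm; interim at 31 per arm with p<0.005; final p<0.048; stated power about 0.83.

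**Step 1: the plan's own figure.** Single look, pooled test:

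power = Φ{[d√n − z√(2p̄(1−p̄))] / √(p₁(1−p₁)+p₂(1−p₂))}, with d = 0.25, n = 62, p̄ = 0.375.

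- d√n = 0.25 × 7.874 = 1.969; √(2 × 0.375 × 0.625) = 0.685; √(0.25 + 0.1875) = 0.661.
- At 0.05: (1.969 − 1.960 × 0.685)/0.661 = 0.947, power 0.828.
- At 0.048: (1.969 − 1.977 × 0.685)/0.661 = 0.929, power 0.824.

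Simulating both looks (400,000 trials) gives 0.835 with the pooled test, 0.839 unpooled and 0.782 with a continuity correction. The stated 0.83 is right for an uncorrected test.

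**Step 2: assumptions.** The documents give no Fitzpatrick distribution and no association with dermatitis, so both are assumed. Skin type has two levels (lighter, darker), and the odds ratio for grade ≥2 (lighter vs darker) runs from 1 to 8. With q the darker share and b the log odds ratio (darker vs lighter), the intercept a in each arm solves (1−q)·expit(a) + q·expit(a+b) = 0.50 or 0.25. The overall rates therefore stay at the plan's values.

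**Step 3: power.** The unadjusted pooled z-test is compared with the stratified (CMH) test, z = Σ(xₖ − n₁ₖmₖ/Nₖ) / √Σ[n₁ₖn₀ₖmₖ(Nₖ−mₖ)/(Nₖ²(Nₖ−1))], both at |z|>1.977, single look, 62 per arm, darker share 20–50%, 100,000 or more trials per setting.

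| Odds ratio | Unadjusted | Stratified | Change (points) |
|---|---|---|---|
| 1 | 0.83 | 0.82 | −1 |
| 2 | 0.83 | 0.83 | about 0 |
| 3 | 0.83 | 0.83–0.84 | 0 to +1 |
| 4 | 0.83 | 0.84–0.86 | +1 to +2.5 |
| 5 | 0.83 | 0.84–0.87 | +1 to +4 |
| 8 | 0.83 | 0.86–0.89 | +2 to +6 |

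The top of each range needs an even split. With a 20% minority, the gain depends on which group is the minority. At an odds ratio of 4 it is about 0.8 points if the minority is the less susceptible group and about 1.5 if it is the more susceptible.

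**Step 4: overall type I error (both arms at 50%).** Unadjusted 0.052–0.054; stratified about 0.046–0.049. Neither varies with the odds ratio. The slightly lower size of the stratified test may explain some of its one-point loss at an odds ratio of 1.

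**Step 5: chance imbalance.** The SD of the between-arm difference in share is √(2q(1−q)/62): √(0.32/62) = 0.072 at q = 0.2 and √(0.50/62) = 0.090 at q = 0.5.

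- A 1.96-SD imbalance moves the risk difference by 1.96 × SD × (difference in risk between skin types). For q = 0.2 and odds ratio 2 (control risks 0.53 and 0.36): 1.96 × 0.072 × 0.17 = 0.024. For q = 0.5 and odds ratio 5 (0.69 and 0.31): 1.96 × 0.090 × 0.38 = 0.067. The planned difference is 0.25.
- An imbalance of 15 points or more means at least 10 patients at 62 per arm (0.15 × 62 = 9.3), probability 3–9%. At 31 per arm it means at least 5 patients (0.15 × 31 = 4.65), probability 15–25%.
- Given such an imbalance at 62 per arm, the unadjusted false-positive rate is about 0.06–0.07 (odds ratio 2), 0.08 (3), 0.10 (4) and 0.11–0.12 (5). Stratified, it stays near 0.05.

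**Step 6: sparse groups at the interim.** Suppose categories V–VI were kept as a separate group with an assumed 5–10% of patients. The chance that at least one arm of 31 has none is 1 − (1 − 0.95³¹)² = 0.37 at 5% and 1 − (1 − 0.90³¹)² = 0.07 at 10%. At a 37.5% event rate, the group has all or no events in 41% to 11% of trials. An ordinary logistic model with three Fitzpatrick groups could therefore fail at that look.

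**The case against.** The strongest case against acting has four parts.

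- **The association is not documented.** No section states or measures a relation between Fitzpatrick category and grade ≥2 dermatitis, and moist desquamation counts as well as erythema. This stands. A reader might infer that the outcome is erythema-based and known to depend on skin type. The documents support only that it could plausibly vary with it.
- **The planned test is sound.** This also stands. Its overall error rate already averages over chance imbalance, and its power is as stated. A reader might infer that leaving out Fitzpatrick biases the test or leaves the trial short of its 0.83. Steps 1 and 4 show neither.
- **The gain may be nil.** This stands for weak association: about zero at an odds ratio of 2 and a one-point loss with none. The claim that adjustment always raises power is not supported.
- **A fine-grained model could break down at 31 per arm, and changing the primary test means redoing the power simulation.** Both are fair. A two-level grouping with a named fallback answers the first, and the second is a real but small cost.

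It can also be said that skin type is recorded only for the baseline table, which is ordinary practice. The protocol does not say so, and this would not explain why the strata are left out as well.

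**Conclusion.** The gap is real but modest. It is a missed, inexpensive improvement and not an error in the plan. Section 14.0 uses neither the two stratification factors nor Fitzpatrick category in the primary comparison, and leaves no pre-specified answer if the arms differ in skin type.

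For skin type, the effect of adjusting ranges from about −1 to +6 power points. Protection against a chance imbalance is the better-supported benefit, but it too grows with the assumed association. All these sizes rest on an assumed two-level factor, assumed shares and odds ratios, and a single look at p<0.048. The value of adjusting for reconstruction and BMI was not quantified, because the documents give no outcome rates by stratum. The case for including them first rests on their being the design's own factors.

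**What to change.** In Section 14.0, pre-specify a covariate-adjusted comparison of the primary outcome:

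- Include reconstruction and BMI group first, then Fitzpatrick category in two levels, with the cut point and the rule for merging sparse categories fixed before unblinding.
- Use a stratified (CMH) test, or a logistic model reported as a standardised risk difference with 95% CI.
- Name a fallback for sparse cells or separation at the 31-per-arm interim, such as penalised logistic regression or a CMH test on the randomisation strata alone.
- Give a rule for missing Fitzpatrick entries.
- Keep the unadjusted two-proportion test alongside, and state which of the two is judged at 0.005 and 0.048, so that there is only one deciding test.

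Also align the time of Fitzpatrick collection: Section 4.2 places it at the History and Physical, which the Section 10.2 schedule puts at consultation, while that schedule puts Fitzpatrick at simulation.

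Cost: no new data, some SAP text and a little modelling; up to about one power point if skin type is not prognostic; and a rerun of the two-look simulation if the adjusted test becomes primary.
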